## x) Urothelial carcinoma (UCC)

- (1) Histologically confirmed, advanced (ie, unresectable or metastatic) transitional cell carcinoma of the urothelium involving the bladder, urethra, ureter, or renal pelvis.
- (2) Not applicable as per Revised Protocol 02
- (3) PD-L1 status must be documented if available.

(4) Participants must have received and progressed/been intolerant of (or not be a candidate for) standard of care chemotherapy (eg, platinum-based regimen) in the recurrent or metastatic setting.

## (5) Not applicable as per Revised Protocol 03

- (6) Must have documented progressive or recurrent disease on or within 3 months of discontinuation of anti-PD-(L)1 therapy (administered as monotherapy or as part of a combination) as per RECIST 1.1 criteria.
  - (a) Prior anti-PD-(L)1 based therapy must be the most recent treatment.
- xi) Squamous Cell Carcinoma of the Head and Neck (SCCHN) (Only Part 1A and Part 1B. Participants with SCCHN will not be allowed in Part 1C.)
  - (1) Histologically confirmed, advanced (ie, unresectable or metastatic) squamous cell carcinoma of the Oral Cavity, Pharynx, Larynx.
  - (2) Not applicable as per Revised Protocol 02
  - (3) PD-L1 status must be documented if available.
  - (4) Participants must have received and progressed/been intolerant of (or not be a candidate for) standard of care chemotherapy (eg, platinum-based regimen) in the recurrent or metastatic setting.
  - (5) For SCC of the oropharynx, HPV status must be documented. Both HPV-positive or HPV-negative participants are permitted in this cohort.
  - (6) Not applicable as per Revised Protocol 03
  - (7) Must have documented progressive or recurrent disease on or within 3 months of discontinuation of anti-PD-(L)1 therapy (administered as monotherapy or as part of a combination) as per RECIST 1.1 criteria.
    - (a) Prior anti-PD-(L)1 based therapy must be the most recent treatment.

### xii) Melanoma in Part 2

- (1) Histologically confirmed, unresectable Stage III or Stage IV melanoma, as specified in the American Joint Committee on Cancer staging system.
  - (a) Participants with ocular or uveal melanoma are ineligible.
- (2) PD-L1 status must be documented if available. PD-L1 status will also be re-tested using tissue acquired from the pre-treatment biopsy (if provided).
- Both BRAF-mutated and wild-type participants are permitted in this cohort.
  - (a) If participant has they must have received (or not be a candidate for) BRAF inhibitor treatment, or declined targeted therapy after having been provided adequate information to make an informed decision.
- (4) Must have documented progressive or recurrent disease on or after discontinuation of anti-PD-(L)1 therapy (administered as monotherapy or as part of a combination) as per RECIST 1.1 criteria:
  - (a) Prior anti-PD-(L)1-based therapy (with at least 6 weeks of exposure) must be the most recent treatment. If the participant received palliative radiation after discontinuation of anti-PD-(L)1 therapy:

(i) The participant meets this criteria if the documented progressive/recurrent disease included sites outside the radiation field.

- (ii) The participant does not meet this criteria if all the sites of progressive/recurrent disease were limited to the field that was subsequently irradiated.
- (b) Participants who received anti-PD-(L)1 in the advanced/metastatic setting, must have documented progressive or recurrent disease on or within 3 months of discontinuation of anti-PD-(L)1 therapy (administered as monotherapy or as part of a combination) as per RECIST 1.1 criteria.
- (c) Participants who received anti-PD-(L)1 in the adjuvant setting must have documented progressive or recurrent disease on or within 6 months of discontinuation of anti-PD-(L)1 therapy (administered as monotherapy or as part of a combination) as per RECIST 1.1 criteria.
- (d) Confirmation of radiographic progression on prior anti-PD-(L)1 therapy is required with a scan confirming progression at least 4 weeks after the initial progression. Screening scans can be used as the confirmation of progression.
- (5) Must not have received prior anti-CTLA-4 therapy.

# 3) Physical and Laboratory Test Findings

Participants must have:

- a) Baseline (only required for Part 1A and Part 1B)
- b) Adequate hematologic function as defined by the following:
  - i) Neutrophils  $\geq 1,500 \mu L$
  - ii) Platelets  $\geq 80 \times 10^3/\mu L$  (transfusion to achieve this level is not permitted within 2 weeks of first study treatment administration)
  - iii) Hemoglobin  $\geq 8$  g/dL (transfusion to achieve this level is not permitted within 2 weeks of first study treatment administration)
- c) Adequate hepatic function
  - i) Alanine aminotransferase (ALT) and aspartate aminotransferase (AST)  $\leq$  3× upper limit of normal (ULN)
  - ii) Total bilirubin  $\leq 1.5 \times$  ULN (except participants with Gilbert's Syndrome who must have normal direct bilirubin)

# iii) Specifically for participants with HCC:

- (1) Prothrombin time-international normalized ratio  $\leq 2.3$  or prothrombin time  $\leq 6$  seconds above control
- (2) Adequate hepatic function as documented by
  - (a) Serum albumin  $\geq 2.8 \text{ g/dL}$  (transfusion to meet this requirement is not permitted)
  - (b) Total bilirubin  $\leq 3 \text{ mg/dL}$
  - (c) AST and ALT  $\leq 5 \times$  the institutional ULN
- d) Normal thyroid function or stable on hormone supplementation per investigator assessment

e) Serum creatinine ≤ 1.5× ULN or creatinine clearance (CrCl) ≥ 40 mL/min (measured using the Cockcroft-Gault formula below):

Female CrCl =  $[(140 - age in years) \times weight in kg \times 0.85]/(72 \times serum creatinine in mg/dL);$ 

Male CrCl =  $[(140 - age in years) \times weight in kg]/(72 \times serum creatinine in mg/dL);$ 

f) Ability to comply with treatment, PK and pharmacodynamic sample collection, and required study follow-up periods.

## 4) Age and Reproductive Status

- a) Males and females, aged at least 18 years old.
- b) Women of childbearing potential (WOCBP) must have a negative serum or urine pregnancy test (minimum sensitivity 25 IU/L or equivalent units of human chorionic gonadotropin) within 24 hours prior to the start of study treatment. An extension up to 72 hours prior to the start of study treatment is permissible in situations where results cannot be obtained within the standard 24-hour window. Additional requirements for pregnancy testing during and after study intervention are located in Section 2, Schedule of assessments.
- c) Women must not be breastfeeding.
- d) WOCBP must agree to follow instructions for method(s) of contraception (Appendix 4) and included in the ICF. WOCBP are permitted to use hormonal contraception methods (as described in Appendix 4).
- e) WOCBP who are continuously not heterosexually active are also exempt from contraceptive requirements but should still undergo pregnancy testing as described in this section.
- f) Not applicable as per Protocol Amendment 04
- g) Not applicable as per Revised Protocol 03
- h) Women who are not of childbearing potential are exempt from contraceptive requirements.
- i) Women participants must have documented proof that they are not of childbearing potential.
- j) The investigator is responsible for review of medical history, menstrual history, and recent sexual activity to decrease the risk for inclusion of a woman with an early undetected pregnancy.
- k) A female participant is eligible to participate if she is not pregnant or breastfeeding, and at least 1 of the following conditions applies:
  - (1) Is not a WOCBP

OR

(2) Is a WOCBP and using a contraceptive method that is highly effective (with a failure rate of <1% per year), with low user dependency, as described in Appendix 4 during the intervention period and for at least 5 months and agrees not to donate eggs (ova, oocytes) for the purpose of reproduction for the same time period

Investigators shall counsel WOCBP, and male participants who are sexually active with WOCBP, on the importance of pregnancy prevention and the implications of an unexpected pregnancy. Investigators shall advise on the use of highly effective methods of contraception (Appendix 4), which have a failure rate of < 1% when used consistently and correctly.

#### 6.2 Exclusion Criteria

### 1) Target Disease Exclusions

- a) Participants with primary CNS malignancies, or tumors with CNS metastases as the only site of disease, will be excluded. Participants with controlled brain metastases; however, will be allowed to enroll. Controlled brain metastases are defined as no radiographic progression for at least 4 weeks following radiation and/or surgical treatment (or 4 weeks of observation if no intervention is clinically indicated), and no longer taking steroids for at least 2 weeks prior to first dose of study treatment, and with no new or progressive neurological signs and symptoms.
- b) Participants with leptomeningeal metastases will be excluded.

### 2) Prohibited Treatments

- a) Cytotoxic agents, unless at least 4 weeks have elapsed from last dose of prior anti-cancer therapy and initiation of study therapy.
- b) Non-cytotoxic agents, unless at least 4 weeks or 5 half-lives (whichever is shorter) have elapsed from the last dose of prior anti-cancer therapy and the initiation of study therapy. If 5 half-lives are shorter than 4 weeks, agreement with the Sponsor/Medical Monitor is mandatory.
- c) Prior participation in an anti-IL-8 clinical study.

### 3) Medical History and Concurrent Diseases

- a) Participants with concomitant second malignancies (except adequately treated non-melanomas skin cancers or in situ urothelial, breast, or cervical cancers) are excluded unless a complete remission was achieved at least 2 years prior to study entry, and no additional therapy is required or anticipated to be required during the study period.
- b) Participants with other active malignancy requiring concurrent intervention
- c) Prior organ allograft
- d) Toxicity (except for alopecia) related to prior anti-cancer therapy and/or surgery, unless the toxicity is either resolved, returned to baseline or Grade 1, or deemed irreversible.
  - i) Any active neuropathy > Grade 2 (NCI CTCAE v4.03)
- e) Participants with the following:
  - i) Active, known, or suspected autoimmune disease:
    - (1) Participants with well controlled asthma and/or mild allergic rhinitis (seasonal allergies) are eligible
    - (2) Participants with the following disease conditions are also eligible:
      - (a) Vitiligo
      - (b) Type 1 diabetes mellitus
      - (c) Residual hypothyroidism due to autoimmune condition only requiring hormone replacement

(d) Euthyroid participants with a history of Grave's disease (participants with suspected autoimmune thyroid disorders must be negative for thyroglobulin and thyroid peroxidase antibodies and thyroid stimulating immunoglobulin (Ig) prior to the first dose of study treatment)

- (e) Psoriasis not requiring systemic treatment, or conditions not expected to recur in the absence of an external trigger are permitted to enroll
- ii) History of life-threatening toxicity related to prior immune therapy or any toxicity that resulted in permanent discontinuation from prior immune therapy (eg, anti-CTLA-4 or anti-PD-(L)1 treatment or any other mAb or drug specifically targeting T-cell co-stimulation or immune checkpoint pathways) except those that are unlikely to re-occur with standard countermeasures (eg, hormone replacement after adrenal crisis).
- iii) Conditions requiring systemic treatment with either corticosteroids > 10 mg daily prednisone equivalents or other immunosuppressive medications within 14 days of study treatment administration. Participants requiring adrenal replacement steroid doses >10 mg daily prednisone equivalent in the absence of active autoimmune disease are allowed.
  - (1) Treatment with a short course of steroids (< 5 days) up to 7 days prior to initiating study treatment is permitted.
- iv) Uncontrolled or significant cardiovascular disease including, but not limited, to any of the following:
  - (1) Myocardial infarction or stroke/transient ischemic attack within the past 6 months
  - (2) Uncontrolled angina within the past 3 months
  - (3) Any history of clinically significant arrhythmias (such as ventricular tachycardia, ventricular fibrillation, or torsade de pointes)
  - (4) History of other clinically significant heart disease (eg, cardiomyopathy, congestive heart failure with New York Heart Association functional classification III to IV [Appendix 10], pericarditis, or significant pericardial effusion)
  - (5) History of myocarditis, regardless of etiology
  - (6) Cardiovascular disease-related requirement for daily supplemental oxygen therapy;
- v) History of chronic hepatitis as evidenced by the following:
  - (1) Positive test for hepatitis B surface antigen
  - (2) Positive test for qualitative hepatitis C viral load by PCR
    - (a) Participants with positive hepatitis C antibody and negative quantitative hepatitis C by PCR are eligible. History of resolved hepatitis A virus infection is not an exclusion criterion.
    - (b) Additional testing or substitute testing per institutional guidelines to rule out infection is permitted.
  - (3) Specific exclusions for participants with HCC:
    - (a) Active coinfection with both hepatitis B and C
    - (b) Hepatitis D infection in participants with hepatitis  $\boldsymbol{B}$

(c) Clinically significant ascites (prior ascites that required treatment and require on-going prophylaxis OR current ascites requiring treatment)

- (4) Presence of portal hypertension with history of bleeding due to esophageal or gastric varices within 6 months prior to randomization
- (5) Episodes of hepatic encephalopathy (≥ Grade 2) within 12 months prior to randomization
- vi) Evidence of active infection that requires systemic antibacterial, antiviral, or antifungal therapy  $\leq 7$  days prior to the first dose of study treatment (except for viral infections that are presumed to be associated with the underlying tumor type required for study entry).
- vii) Known history of testing positive for human immunodeficiency virus (HIV) or known acquired immunodeficiency syndrome. Note: Testing for HIV must be performed at sites where mandated by local requirements.
- viii) Any major surgery within 4 weeks of the first dose of study treatment. Participants must have recovered from the effects of major surgery or significant traumatic injury at least 14 days before the first dose of study treatment.
- ix) Receipt of a live/attenuated vaccine within 30 days of first treatment
  - (1) The use of inactivated seasonal influenza vaccines, eg, Fluzone®, will be permitted on study without restriction.
- x) Receipt of packed red blood cells or platelet transfusion within 2 weeks of the first dose of study treatment
- xi) Any known or underlying medical, psychiatric condition and/or social reason that, in the opinion of the investigator or Sponsor, could make the administration of study treatment hazardous to the participants or could adversely affect the ability of the participant to comply with or tolerate the study.
- f) WOCBP who are pregnant or breastfeeding.
- g) Previous SARS-CoV-2 infection within 10 days for mild or asymptomatic infections or 20 days for severe/critical illness prior to C1D1.
  - i) Acute symptoms must have resolved and based on investigator assessment in consultation with the Medical Monitor, there are no sequelae that would place the participant at a higher risk of receiving study treatment.
- h) Previous SARS-CoV-2 vaccine within 14 days of C1D1.
- i) History of hemophagocytic lymphohistiocytosis (HLH)/macrophage activation syndrome (MAS)
- j) A history of disease related to chronic Epstein-Barr virus (EBV) infection including post-transplant lymphoproliferative disorders, Hodgkin's lymphoma, extranodal natural killer (NK)/T-cell lymphoma (nasal type), Burkitt's lymphoma, and chronic active EBV infection.

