# vii) Not applicable as per Protocol Amendment 04: Pancreatic ductal adenocarcinoma viii) Hepatocellular carcinoma (Part 1C only)

- (1) Participants cannot be eligible for liver transplant at the time of inclusion. For participants who progressed after locoregional therapy, locoregional therapy for HCC must be completed at least 4 weeks prior to the baseline scan. All acute toxic effects of any prior local treatment must have resolved to National Cancer Institute (NCI) Common Terminology Criteria for Adverse Events (CTCAE) v4.03 Grade > 1 or been deemed irreversible.
- (2) Participants may either have histologically or radiologically confirmed HCC. Participants with a radiological diagnosis may be enrolled for screening in the study but histological confirmation is mandatory prior to initiation of study therapy.
- (3) Participants must have received and progressed/been intolerant of (or not be a candidate for) at least 1 line of therapy, including anti-PD-(L)1-based therapy.
  - (a) Prior anti-PD-(L)1-based therapy must be the most recent treatment
- (4) Must be Child-Pugh Class A (6 points or less) (Appendix 9);
- (5) Must have results of testing for hepatitis B surface antigen, hepatitis B surface antibody, hepatitis B core antibody, hepatitis B deoxyribonucleic acid (DNA) PCR, hepatitis C antibody and hepatitis C ribonucleic acid (RNA) PCR;
- (6) For participants with hepatitis B infection, hepatitis B DNA viral load must be < 500 IU/mL and the participant must be on anti-viral therapy per institutional guidelines.
  - (a) If the participant is receiving anti-viral therapy, the anti-viral therapy must have been started at least 4 weeks prior to screening.
- (7) Participants with hepatitis B infection cannot have a co-infection with hepatitis C or hepatitis D (must obtain hepatitis D antibody testing).
- (8) Participants with active hepatitis C virus (HCV), infection, as defined by any detectable HCV RNA and positive antibody titer, can be enrolled provided they are on anti-viral therapy. Participants with resolved HCV infection, as evidenced by undetectable HCV RNA and positive antibody titer, can be enrolled. Participants on antiviral therapy for HCV should continue treatment during the study. Participants with active HCV who are not on antiviral therapy at screening cannot be enrolled in the study.
  - (a) If the participant is receiving anti-viral therapy, the anti-viral therapy must have been started at least 4 weeks prior to screening.

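### Exclusion 3)e)v)(2) bars HCV PCR-positive participants with no HCC exemption, while HCC inclusion 2)c)viii)(8) admits viremic HCV on antiviral therapy

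*Combined protocol and SAP*

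**What the plan says.** Section 6.2, exclusion 3)e)v), covers a history of chronic hepatitis and has no tumor-type limit at its head. Under it:

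- v)(1): "Positive test for hepatitis B surface antigen".
- v)(2): "Positive test for qualitative hepatitis C viral load by PCR". Sub-item (a) gives relief: "Participants with positive hepatitis C antibody and negative quantitative hepatitis C by PCR are eligible". Sub-item (b) permits additional or substitute testing to rule infection out.
- v)(3): further exclusions specific to HCC, including coinfection with hepatitis B and C, and hepatitis D in those with hepatitis B.

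Section 6.1, inclusion 2)c)viii), applies to HCC in Part 1C only:

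- Item (5): "Must have results of testing for hepatitis B surface antigen, hepatitis B surface antibody, hepatitis B core antibody", followed by hepatitis B DNA, hepatitis C antibody and hepatitis C RNA.
- Item (6): "For participants with hepatitis B infection, hepatitis B DNA viral load must be" below 500 IU/mL, with antiviral therapy also required.
- Item (7): "Participants with hepatitis B infection cannot have a co-infection with hepatitis C or hepatitis D".
- Item (8): active HCV, "as defined by any detectable HCV RNA and positive antibody titer, can be enrolled provided they are on anti-viral therapy". The converse is also stated: "Participants with active HCV who are not on antiviral therapy at screening cannot be enrolled in the study".

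Section 6 says that no exceptions to the entry criteria are granted, the close of Section 6.2 asks that all of them be fully met, and Section 9 disallows waivers.

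**The concern.** Item (8) defines active HCV by the finding that v)(2) treats as disqualifying, then admits it under treatment. Sites apply both lists to the same participant. A site that follows v)(2) turns away someone the HCC criteria were written to let in. A site that follows item (8) enrolls someone who fails a stated exclusion, which can be recorded as an eligibility deviation.

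The situation is foreseeable. Table 9.1.4-1 orders hepatitis C RNA PCR at entry for HCC participants, whereas the general serology panel names only hepatitis B surface antigen and hepatitis C antibody. The protocol thus requires the triggering test in the group that item (8) addresses. The question can also return after entry, because Section 8.1.1 makes treatment beyond progression conditional on still meeting the other eligibility criteria.

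**Working it through.** No arithmetic applies and the plan gives no figure to reproduce. The check takes each relevant type of HCC participant through both rules.

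| HCC participant | Section 6.1, 2)c)viii) | Section 6.2, 3)e)v) | Result |
|---|---|---|---|
| HCV antibody positive, RNA quantifiable, on antivirals | (8) admits | (2) excludes; (a) does not reach this participant | Direct conflict |
| HCV antibody positive, qualitative PCR positive, quantitative PCR negative, on antivirals | (8) admits | (2)(a) makes eligible | No conflict |
| HCV antibody positive, RNA undetectable | (8) admits as resolved | (2) not triggered | No conflict |
| HCV antibody positive, RNA quantifiable, not on antivirals | (8) bars | (2) excludes | Consistent |
| Surface-antigen positive, HBV DNA < 500 IU/mL, on antivirals | (6) admits, if this counts as hepatitis B infection | (1) excludes | Conflict on that reading only |
| Surface-antigen negative, classed as hepatitis B infection on another marker, DNA < 500 IU/mL, on antivirals | (6) admits | (1) not triggered | No conflict |

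The next step is to look for text that resolves the first row.

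1. v)(2)(a) needs a negative quantitative PCR, so it does not help a participant with quantifiable RNA. v)(2)(b) concerns ruling infection out, which does not apply when infection is present.
2. v)(3) is framed as exclusions specific to HCC. It adds conditions and waives neither (1) nor (2).
3. The exception for viral infections associated with the tumor type belongs to item vi), on active infection needing recent systemic treatment. It does not extend to item v).
4. The eligibility text contains no rule that a specific inclusion overrides a general exclusion, and Sections 6 and 9 rule out exceptions and waivers.

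Nothing resolves the first row. The fifth row depends on the meaning of hepatitis B infection, which item (6) leaves undefined. Item (5) requires a surface-antigen result among several markers. That makes the surface-antigen reading reasonable but does not establish it.

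**The case against.** The strongest answer is that HCC-specific text routinely displaces general hepatic rules in this protocol, and item (8) is simply the HCC rule for HCV. At entry, AST/ALT may reach 5x ULN in HCC against 3x otherwise, and the bilirubin limit becomes 3 mg/dL instead of 1.5x ULN. Section 7.6.3.1 sets separate dose-delay rules. Section 9.2.8 defines potential drug-induced liver injury at ALT above 10x ULN in HCC against ALT or AST above 3x. The general AST/ALT limit carries no wording to exempt HCC either. If v)(1) and v)(2) applied to HCC, the coinfection and hepatitis D bars in v)(3) and item (7) would be nearly redundant. HCC has a fuller screening panel, item vi) shows that the drafters expected tumor-associated viral infection, and the Amendment 04 change log records that the HCC inclusion criteria and v)(3) were revised together.

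This stands as evidence of intent: v)(1) and v)(2) were probably written for non-HCC participants. It does not supply the exemption. In the entry-laboratory and liver-injury examples, the HCC value follows the general rule in the same section under an HCC label. Here the two rules sit in separate lists, both of which must be satisfied, and the HCC part of the exclusion list gives no replacement rule for surface antigen or HCV PCR.

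Two limits raised on the other side are also right. v)(2) does not bar every positive HCV PCR, because (a) admits antibody-positive participants with a negative quantitative result. And a hepatitis B conflict that rests on an undefined term is not demonstrated.

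**Conclusion.** The hepatitis C contradiction is real for HCC participants in Part 1C with quantifiable viremia on antiviral therapy. It is a minor drafting fault in an operative eligibility rule, with recoverable intent. The hepatitis B conflict is secondary and holds only if hepatitis B infection in item (6) includes surface-antigen-positive disease.

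A reader might infer more, and the documents do not support it:

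- They do not show that anyone was wrongly enrolled or turned away. They give neither the number of HCC participants affected, nor the reading that sites used, nor whether HCC enrollment is closed.
- They do not show any effect on the randomized comparison. Part 2 enrolls melanoma only, so its objective response rate analysis is untouched.

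The conclusion assumes that both lists bind as written, as Sections 6, 6.2 and 9 state.

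**What to change.** Add to v)(2), and for consistency to v)(1): *does not apply to participants with HCC, who must satisfy inclusion 2)c)viii)(5)-(8) and must not have any condition listed in exclusion v)(3)*. The second half needs the negative form, because wording that asks participants to meet an exclusion would literally require the excluded condition. The same clause would govern any later eligibility re-check under Section 8.1.1.

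The cost is one clause, used twice, in Section 6.2. Design, sample size and analysis do not change. If HCC enrollment has closed, a note recording which reading was applied would serve instead.
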